## **2. Pressure pain threshold (PPT):**

The procedure will be explained to the participant prior administration of the algometer and Measurement will be by Wagner base line algometry. Then the therapist will instruct the patient to recline in supine position. The investigator will palpate and mark the tender point over the medial tuberosity of the calcaneous. After that, therapist will apply the algometry

over the mark placed on the medial tuberosity of the calcaneus. The algometer contact head will aligned perpendicularly to the tender point, with the investigator gradually increasing the algometer force until the patient reported pain. The algometer reading will recorded in newton's. Higher algometer scores indicate greater force tolerance and, thus, less tenderness. Lower algometer readings indicate less force tolerance and, thus, greater heel tenderness. The reliability and validity of the algometer as a subjective outcome measure of tenderness has been supported in various studies (see **Fig. 14**). (Wibowo et al., 2017) (Sangam et al., 2015)(Alotaibi et al., 2015)

**Figure 14** WAGNER FDX 50 algometer

### 3. Pain intensity level assessment:

- Each patient will be instructed to mark his/her level of pain on visual analogue scale. Then, the distance will be measured by ruler in

millimeter (mm) from 0 direction and recorded in patient file. See in Appendix III (**Janusz, 2017**).

#### **4. Activity of daily living:**

- Foot and Ankle Ability Measure (FAAM) scale will measure disability: which is a self-report outcome instrument developed to assess physical function for individuals with foot and ankle related impairments. Patient will choose from (0-4) where zero mean unable to do and four mean no difficulty (see appendix II). This instrument includes two subscales:
  - a. Activities of Daily Living (ADLs) subscale of 26 items
  - b. Sports subscale of 8 items

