Shockwave could be used as a pretreatment of cell membranes for electroporation. The Shockwave possible role of multiple Nano bubbles was examined. It has also been shown that not only would the multiple Nano bubbles make it possible to create larger pores, but also increase the pore density on the surface. The multi-pore scenario would be useful practically in enhancing material throughout into cells. (**Hu et al., 2019**).

Direct and indirect Shockwave effects described concerning stone disintegration could also contribute to transient increase membrane permeability on application of low energy shockwave to eukaryotic cell membranes. Low energy shockwave can deliver macromolecules of up to 2,000,000 molecular weight into the cytoplasm of cells. (**Tyagi & Chuang, 2018**).

Low energy shockwave has a significant effect on the permeability of tissue. Consequently, it might be used to deliver substance such as Acetic acid. Accordingly, Shockwave might help to improve the outcomes with calcaneal spur patients. Therefore, the present study might help in treatment of calcaneal spur patient and might improve the quality of life in fast and efficient way.

➤ **Delimitations:**

This study will be delimited to calcaneal spur patients, selected from outpatient clinics at faculty of physical therapy on Beni-Suef University on the following criteria:

1. The patient's age ranged from 30 to 65 years
2. Patients with calcaneal spur.
3. Patients with intact sensory perception.
4. At least 6 weeks from last corticosteroid injection; 4 weeks from the last local anesthetic injection, iontophoresis, ultrasound, and electrotherapy (**Gerdesmeyer et al., 2008**)
5. X-Ray will be used to measure the length of calcaneal spur.
6. Algometry will be used to measure Pain pressure threshold.
7. Visual Analogue scale will be used to measure Pain intensity level.
8. Foot and Ankle Ability Measure (FAAM) questionnaire will be used to measure physical function.

➤ **Basic Assumptions:**

The following assumptions are necessarily for the development of the study:

- The instructions that will give to all patients for assessment should be accurately, clearly, and faithfully followed.
- All patients will be cooperative during the assessment and treatment procedures.

➤ **Hypothesis:**

The null hypotheses of this study stated as the following:

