- $H_0$  : there is no statistical significant effect of the use of extracorporeal acetic acid shockwave phonophoresis on length of calcaneal spur, pain pressure threshold, pain intensity level and physical function in patients with calcaneal spur.
- $H_0$ : there is no statistically significant effect of the use of extracorporeal Shockwave on length of calcaneal spur, pain pressure threshold, pain intensity level and physical function in patients with calcaneal spur.
- $H_0$ : there is no statistically significant difference between extracorporeal shockwave versus acetic acid shockwave phonophoresis on length of calcaneal spur, pain pressure threshold, pain intensity level and physical function in patients with calcaneal spur.

➤ **Definition of terms:**

The following terms defined for clear understanding of the terminology used in the presented study:

**Calcaneal spur:** is an osteophyte outgrowth just medial process of calcaneal tuberosity.

**Shockwave:** is an acoustic wave characterized by high positive pressures of more than 1000 bar (100 MPa), which can be developed within an extremely short rise time ( $10^{-9}$  seconds) and followed by a low-pressure phase of tensile stress equivalent to 100 bar (10 MPa).

**Energy flux density:** is a term used to reflect the amount of energy delivered to a specific area of tissue. measured in (Mj/mm^2) (**Speed C , 2014**)

**Enthesis** is the site of attachment of tendon, ligament, fascia, or capsule to bone.

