### **a. Evaluative Equipment:**

1. X-ray Machine: The best method of assessment of skeletal structure of foot by using radiographic techniques, which considered as the gold standard for assessment bone deformity and alignment of foot in weight bearing position. It will used to scan the foot and calcaneus before and after treatment; it consists of operating console of x ray machine, x ray tube, x ray cassette, digital radiography systems and desktop computer with windows operating system to measure the length and width of the calcaneal spur. (**Rajakaruna et al., 2015**).
2. Pressure pain threshold (PPT): A handheld pressure algometry will be used to measure heel tenderness threshold. The threshold is the minimum force required producing the sensation of pain. The PA is a force gauge equipped with a rubber tip and calibrated in kg/cm^2 (Model FDX, Algometer, WAGNER instruments, Greenwich, CT) (**Alotaibi et al., 2015**).
3. Visual analogue scale (VAS): are used to express the severity of illness (usually pain) by patients by making a mark determining a decimal number from 0 to 100 (mm) on line with 'no pain' to the left and sever pain could be to the right. The subjects rated their perception of pain by making a mark on the VAS line. The distance from the left to the mark will measured and the accuracy will adjusted to one decimal place (see appendix III) (**Kamper, 2012**).

4. Foot and Ankle Ability Measure (FAAM): is a self-report measure that assesses physical function of individuals with lower leg, foot, and ankle musculoskeletal disorders. FAAM is assess activity of daily living ADLs (26 items) and sport activity (8 items). (**Irrgang M et al., 2005**). FAAM is a reliable, responsive, and valid measure of physical function for individuals with a broad range of musculoskeletal disorders of the lower leg, foot, and ankle (**see appendix II**) (**Martin et al, 2005**).

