### **A. Measurement methods:**

Before starting the study, a consent form will be taken from each participant in this study as an agreement to be included in the present study. Each participant will examined medically to exclude any abnormal medical problem, which previously mentioned. Measurement will taken pretest assessment and posttest assessment and post one month follow up as follow:

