## **Statistical Analysis:**

- All analysis will be carried out using the statistical package SPSS V.25.00 (IBM Corporation).
- Data will be expressed as mean and SD or median (in case of violation of normality) for continuous variables and as percentages for categorical data.
- The Shapiro-Wilks test will be used to test the normality of the data.
- 2-way mixed Design MANOVA will be used to compare the groups for normally distributed data.
- 2-way mixed Design MANOVA will be used to compare the groups for normally distributed data.
- Kruskal Wallis and Mann-Whitney tests will be used to compare the groups for non-parametric and not normally distributed data.
- Age and gender will be considered as an independent variable.
- Pairwise multiple comparisons will be performed using the Bonferroni correction test.
- All tests are two-sided, and statistical significance will be set at  $p<0.05$ .

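### Does the plan leave open which FAAM score is the physical-function outcome, and does the 26-versus-21 item count matter?

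*Combined protocol and SAP*

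**What the plan says.** The Delimitations list states that the "Foot and Ankle Ability Measure (FAAM) questionnaire will be used to measure physical function". Each of the three null hypotheses under Hypothesis includes physical function beside spur length, pressure pain threshold and pain intensity.

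Section 6.A.4, headed as activity of daily living, says the "Foot and Ankle Ability Measure (FAAM) scale will measure disability" and then describes it as an instrument for physical function. Items are rated 0 to 4, with zero for inability and four for no difficulty. It continues: "This instrument includes two subscales". The first is the "Activities of Daily Living (ADLs) subscale of 26 items"; the second is a sports subscale of 8. Section 5.a, item 4, repeats both counts and cites the instrument's validation paper.

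Appendix II supplies two pages, both titled as the ADL subscale. They carry rated rows, an N/A column separate from the column for inability, and one 0-100 rating of usual daily function. Appendix III follows in the supplied text.

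The Statistical Analysis section says "2-way mixed Design MANOVA will be used to compare the groups for normally distributed data". It adds rank tests for non-normal data and Bonferroni for pairwise comparisons, and lists no dependent variables.

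**The concern.** One named outcome seems to have three possible scores: ADL subscale, sports subscale and 0-100 rating. The Statistical Analysis section does not choose among them, and its Bonferroni rule concerns pairs of groups, not a choice among scores. If the score were picked once results were known, the false-positive rate would rise and a reader could not tell that it had.

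The item counts appear to confirm a loose definition, since the text and the form disagree. The N/A column adds a further worry. A mixed-design MANOVA as usually run needs every outcome at every visit, so a FAAM score lost to one N/A answer could remove a patient's other outcomes too.

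**Working it through.** **Item count.** Stated in 5.a and 6.A.4: 26 + 8 = 34. Counted in Appendix II: 15 rows on the first page + 6 on the second = 21, all ADL (22 with the 0-100 rating). Neither 21 nor 22 matches 26 or 34. The ADL shortfall is 26 − 21 = 5. The 8 sports items are absent from the supplied text, but a page may have been lost in reading the PDF, so their absence carries little weight.

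**Does the count reach a result?** No formula in the plan uses 26. Take the worst clerical outcome: the 21-item sum (maximum 21 × 4 = 84) is divided by the maximum for 26 items (26 × 4 = 104). Every score is multiplied by the same constant, 84/104 = 0.81. F statistics, t statistics and ranks do not change when a variable is rescaled by a constant. Reported means would be too low by that factor, but no test would change.

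**Which score?** Set side by side, the places that bear on the choice are:

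| Place | Points to |
|---|---|
| Heading of 6.A.4 | ADL |
| Both pages of Appendix II | ADL |
| 6.A.4 and 5.a, text | describe both subscales, choose neither |
| 0-100 rating | a line on the form, absent from the methods |
| Statistical Analysis | silent for all outcomes |

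The ADL subscale is implied, though not stated. The rating is a weak candidate, because the methods describe only 0-4 items in two subscales. If sports data are also collected, a MANOVA can carry both subscales as dependent variables, with no selection.

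**Size if a score were picked after the fact.** Simulation with no true effect, 20 per group, two-sample t-test, smallest p-value of k correlated scores, 100,000 runs. The correlations of 0.8 to 0.5 are assumed.

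| Scores | Each pair tested at 0.05 | Each pair at 0.05/3 = 0.0167 |
|---|---|---|
| 1 | 5% | 1.7% |
| 2 | about 8% to 9% | 2.7% to 3.1% |
| 3 | about 10% to 12.5% | 3.6% to 4.4% |

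The right-hand column applies if there are three groups and Bonferroni covers their three pairs. Both columns need a post hoc choice that the plan does not describe.

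**N/A answers.** Coding N/A as 0 would cost at most 4/84 = 4.8 points per item on a 0-100 scale. But 6.A.4 reserves zero for inability, and the form gives inability and N/A separate columns, so that coding would contradict the plan's own definitions. Treating any N/A as a missing total would, if an assumed 5% to 20% of patients mark one, remove 0.05 × 60 = 3 to 0.20 × 60 = 12 patients from the MANOVA (2 to 8 of 40). No rule in the plan calls for this, and the shares are guesses. The ordinary treatment, 100 × sum / (4 × items answered), loses nobody who answers some items.

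**The case for a change.** The strongest case for a change is that a citation can supply a scoring rule but cannot say which subscale is this trial's outcome. The silence is real: physical function stands in all three hypotheses, and no dependent variable is listed. A lost sports page would not explain 21 ADL items against 26. A few sentences would settle it at no burden to patients. The Subjects section also gives both forty patients in two groups and three groups of 20. If there are two groups there is one pair, Bonferroni gives no reduction, and the 5% column applies.

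What stands is that the ADL score is implied and not written down, that the N/A rule is left to the instrument, and that 26 does not match the form. The two-group reading does raise the conditional error rates. It does not supply the missing premise, which is selection after the data are seen. The lack of a named variable and visit runs through the whole Statistical Analysis section and is not peculiar to the FAAM.

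**Conclusion.** The facts behind the concern are right, but they do not call for a change to the plan. No stated rule produces a wrong result. An analyst with this protocol would score the ADL subscale from the form supplied, follow the cited instrument for scoring, and leave N/A items out of the sum and the denominator. The 26-versus-21 mismatch is a clerical slip of 5 items with no effect on any test.

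The inflated error rates (up to about 12.5% per pair at the 5% level, or 4.4% under Bonferroni for three pairs) depend on assumed correlations and on a post hoc choice that the plan does not make. The patient losses depend on assumed N/A shares and a coding the plan does not adopt. The conclusion rests on reading the 6.A.4 heading and the ADL form together. If a sports form is in use as well, analysing both subscales would still need no selection.

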### **B. Therapeutic methods:**

#### **1. Shockwave therapy:**

- The shockwave will be applied for both group:
  - a. Group A: Shockwave (with 5% Acetic acid gel).
  - b. Group B: Shockwave (with ultrasound coupling medium gel).
  - c. Group C: conventional physical therapy program (Exercise).
- Once per week for 6 weeks for Shockwave.
- The intensity of Shockwave adjusted according to highest energy flux density the patient can tolerate. To achieve the best improvement in pain relief, the energy level of ESWT will adjusted to the maximum level that patients can tolerate the pain induced by ESWT
- Application at the most painful sit on Calcaneus.
- Total Energy flow density will calculated (as the product of the number of treatment sessions, the number of impulses per treatment session and the EFD of the impulses)(**Schmitz et al., 2015**).

## **1. Exercise program:**

### **a. Stretching exercise:**

- Standing calf-stretching exercise: stretching gastrocnemius & Soleus and Posterior Tibialis Muscle stretch muscle: In sitting and standing position for 15-30 seconds and Repeat three times.
- Towel stretch: stretching exercise for planter fascia in sitting and standing position for 15-30 seconds (Repeat three times)
- Ice bottle applied as a home advice to stretch intrinsic foot muscles and analgesic effect.

### **b. Strengthening exercise:**

- Some authors suggest that calcaneal length related to the dorsal and plantar flexor muscle strengths, which in turn affect the foot and lead to abnormal loading which increase the susceptibility for injury and pain (**Sonu & Aman, 2015**) (**Büyükтурان, 2017**).
- Towel pickup exercise to strengthen intrinsic muscles of the foot
- Marble pickups exercise: patients will be instructed to collect 10 marbles from ground, by toes, and put it in a bowl and repeat it (3sets).
- Calf raises exercises
- Static and dynamic balance exercise.

## **2. Advices:**

- Advices to alter calcaneal spur pain: rest, modified shoes, modified activity, use ice cubes regularly.
- Dietary advices to decrease gout and adjust body weight.

## **Data collection:**

In this study, data collection will be conducted via data collection sheet and then the data will be collected in large table to form raw data that will be used as base for statistical analysis.

## **Statistical Analysis:**

- All analysis will be carried out using the statistical package SPSS V.25.00 (IBM Corporation).
- Data will be expressed as mean and SD or median (in case of violation of normality) for continuous variables and as percentages for categorical data.
- The Shapiro-Wilks test will be used to test the normality of the data.
- 2-way mixed Design MANOVA will be used to compare the groups for normally distributed data.
- 2-way mixed Design MANOVA will be used to compare the groups for normally distributed data.
- Kruskal Wallis and Mann-Whitney tests will be used to compare the groups for non-parametric and not normally distributed data.
- Age and gender will be considered as an independent variable.
- Pairwise multiple comparisons will be performed using the Bonferroni correction test.
- All tests are two-sided, and statistical significance will be set at  $p<0.05$ .

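### With no analysis set or missing-data rule, the mixed-design MANOVA defaults to complete cases: a patient missing one modelled measurement loses every recorded value

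*Combined protocol and SAP*

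**What the plan says.** The Statistical Analysis section lists one parametric between-group method, and lists it twice: "2-way mixed Design MANOVA will be used to compare the groups for normally distributed data". The alternative for other data is "Kruskal Wallis and Mann-Whitney tests will be used to compare the groups for non-parametric and not normally distributed data", with a Shapiro-Wilk test choosing between them. The software is fixed: "All analysis will be carried out using the statistical package SPSS V.25.00 (IBM Corporation").

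The visits are in section 6.A, Measurement methods: "Measurement will taken pretest assessment and posttest assessment and post one month follow up as follow". The four outcomes (spur length, pressure pain threshold, pain intensity, physical function) are named in the Hypothesis section and described in the sections on X-ray, pressure pain threshold, pain intensity and activity of daily living. The X-ray section requires a minimum of two films, one before and one after treatment. It does not assure a film at one month.

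No section defines an analysis set, states that patients are analysed in the group to which they were randomised, gives a rule for missing values, or says whether patients who stop sessions are still measured. The Data collection section says only that values are entered in a table. The nearest statement is in Basic Assumptions in Chapter I: "All patients will be cooperative during the assessment and treatment procedures".

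**The concern.** A two-way mixed MANOVA treats each patient's set of measurements as one response vector. If one element is missing, the whole patient leaves the model, including the pretest and posttest values already in hand. With nothing in the plan to prevent this, the parametric comparison is made among patients with complete records.

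Two things are at stake. If the reason for missing a visit is related to outcome and differs between arms, completers are no longer comparable as randomised, and the arm that loses more poor responders looks better. Even if loss is random, recorded data are thrown away in a trial with 20 patients per arm.

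The analysed patients also depend on the normality test. A Kruskal-Wallis or Mann-Whitney test at a single visit uses everyone present at that visit; the MANOVA uses only those present throughout. The Shapiro-Wilk result would therefore decide who is analysed as well as which test is used.

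**Working it through.** **The plan's own figures.** There is no sample-size calculation, loss rate or SD to reproduce. The arm size of 20 is from the Subjects section. The SDs, correlations and loss rates below are assumptions.

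**1. Does the method drop whole patients?** A MANOVA was fitted in Python (not SPSS) to 60 simulated patients with 12 responses (4 outcomes × 3 times). Six patients each had one missing value. The model kept 54 patients, so 6 missing cells removed 6 whole patients and their 11 other values each.

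How much is lost depends on whether all outcomes enter one model, which the plan does not say. If they do, and each cell is independently missing with probability m, the complete share is (1 − m)^12:

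| m | complete share |
|---|---|
| 1% | 89% |
| 2% | 79% |
| 5% | 54% |

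A three-visit joint model that includes spur length could also lack the one-month film by design.

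**2. Random loss.** Let a be the chance of missing each of the two post-treatment visits. Complete patients per arm = 20(1 − a)². The standard-error factor against no loss is 1/(1 − a). Using everyone present at a visit, the factor is 1/√(1 − a).

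| a | complete of 20 | present per visit | SE, complete cases | SE, all present | excess from deletion |
|---|---|---|---|---|---|
| 5% | 18.1 | 19 | 1.053 | 1.026 | 2.6% |
| 10% | 16.2 | 18 | 1.111 | 1.054 | 5.4% |
| 15% | 14.5 | 17 | 1.176 | 1.085 | 8.5% |

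At 10%, standard errors are about 11% wider than with no loss. About 5% is the avoidable part, because no method recovers visits that were never made. At two-sided 0.05 and 80% power, the detectable difference (1.96 + 0.84)·√(2/n) rises from 0.89 SD at n = 20 to 0.99 SD at n = 16.

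**3. Outcome-related loss in one arm.** Assume a posttest VAS SD of 20 mm, a posttest to one-month correlation of 0.6, no true effect, and that the k patients of 20 with the worst posttest pain miss the one-month visit. The fall in that arm's posttest mean is SD × (sum of the k largest expected normal order statistics for n = 20)/(20 − k).

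- k = 4: the sum is 5.327, and 5.327/16 = 0.333. Then 0.333 × 20 = 6.66 mm (5.0 mm at SD 15, 8.3 mm at SD 25). At one month, 0.6 × 6.66 = 4.0 mm (2.0 to 5.3 mm for correlations 0.3 to 0.8).
- k = 2: the sum is 3.275, and 3.275/18 = 0.182. Then 0.182 × 20 = 3.6 mm, and 0.6 × 3.64 = 2.2 mm at one month.

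**4. Does keeping partial data remove this?** A large simulation used the same correlation, 20% loss tied to the posttest value in one arm, 20% random loss in the other, and a true difference of zero. Completers gave −0.35 SD at posttest and −0.21 SD at one month. Using all posttest values, and predicting one month from pretest and posttest, gave 0.00 SD at both.

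**The case against.** The plan never states a completer analysis. It is the default of the named method, and imputation beforehand is unplanned but not excluded. That is true, but it leaves the choice until the data are seen.

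A reader might infer that anyone who stops treatment is removed. The documents do not support this. The MANOVA drops missing measurements, not stopped treatment, and a patient who abandons sessions but attends all three assessments stays in. The gap is that the plan does not say whether such patients are assessed.

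A reader might also infer that loss will be frequent and unequal between arms, because "the energy level of ESWT will adjusted to the maximum level that patients can tolerate the pain induced by ESWT". This does not hold for the only between-group hypothesis, shockwave with acetic acid gel against shockwave alone. Both arms have their intensity set in the same way and differ in the gel. Tailoring to individual tolerance is not evidence that patients will stop. The argument could reach only the exercise group, which appears in no hypothesis and conflicts with the statement of forty patients in two groups; those passages need reconciling separately.

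The 6.7 mm figure is a deliberately one-sided case: the worst patients in one arm are lost and nobody in the other. It shows what the method permits and does not predict what will happen.

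Finally, separate models give up the omnibus test across outcomes, and the plan's only correction, "Pairwise multiple comparisons will be performed using the Bonferroni correction test", does not cover four outcomes. This stands, and the remedy has to deal with it.

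**Conclusion.** The point holds as a default of the named method that the plan does nothing to prevent. Any patient missing a modelled measurement leaves the parametric comparison with all recorded values, and the normality test changes which patients are analysed. It does not hold as a claim that treatment stoppers are excluded or that unequal loss is to be expected.

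The size cannot be derived from the documents. Under the stated assumptions, selective loss of 2 to 4 of 20 patients in one arm shifts its mean by about 3.6 to 6.7 mm at posttest and 2.2 to 4.0 mm at one month. Random loss of 10% per visit costs about 5% in standard error beyond what the missed visits themselves cost. If nobody misses a modelled measurement, the problem does not arise. A better method is available cheaply in the same software, so the plan should change before patients are lost, because assessments not made cannot be recovered.

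**What to change.** **Measurement methods (6.A).** State that all randomised patients, including those who stop or miss sessions, are invited to the posttest and one-month assessments and are analysed in their allocated group.

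**Statistical Analysis.**
- Replace the MANOVA with a linear mixed model for repeated measures for each outcome (SPSS MIXED): arm, visit and arm-by-visit, unstructured covariance, all three visits as responses, age and gender retained as the plan has them.
- Make this the main analysis whatever the Shapiro-Wilk result. Keep the rank tests and the complete-case MANOVA as sensitivity analyses.
- Fit spur length only at the visits where an X-ray is planned, and state which those are.
- State a multiplicity rule across the four outcomes, for example Holm, because the omnibus test is given up.
- Report stops, missed visits and reasons by arm.

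**Cost.** A few sentences, a different procedure in the package already named, one model per outcome, a multiplicity adjustment, and contact with patients who stopped. The mixed model is valid only if loss depends on observed values; it does not protect against loss driven by values never recorded, which is why reasons should be reported.

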#### **1. Design of the study:**

Double-blinded pretest posttest randomized control design will used.

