#### **2. Subjects:**

The age of participant will range from 30 to 65 years. These patients will be allocated from the outpatient clinic in faculty of physical therapy at Beni-Suef University. The purpose, nature and potential risk of the study will be explained to all participant and they will sign a written informed consent prior to participation (**Appendix I**). Forty patients from both gender will be involved in this study and will randomly subdivided into two equal groups in number:

**Group (A):** (experimental group 1) this group composed of 20 subjects represented the experimental group 1. They will receive 6 sessions acetic acid shockwaves phonophoresis with Time between sessions 5-7 days plus exercise and dietary advice.

**Group (B):** (experimental group 2) this group composed of 20 subjects and represented the experimental group 2 who will receive 6 sessions of Shockwave plus exercise and dietary advice.

**Group (C): (Control Group):** This group composed of 20 subjects they will take conventional physical therapy program (Exercise)

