#### **1. X-ray:**

Lateral calcaneal x-ray helps to evaluate bony conditions of the foot for example, Calcaneal spur, calcaneal stress fractures may be visualized on lateral calcaneal and that help in excluding any condition not suitable with

this research. Each patient should do at least two x-rays ,one before and another after, computer aided linear measurements will recorded for spur length and width in (mm) from tip to base as defined by a line determining the calcaneal border as described by many authors (**Fig. 13**) (**Kuyucu et al.,2015**)(**Büyükturan, 2017**) (**Gladman et al., 2014**)

*Figure 13 : X-ray machine*

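### The plan does not say which term of the mixed MANOVA tests treatment; read literally it is the group main effect, which averages in the pretest and dilutes the treatment difference

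*Combined protocol and SAP*

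**What the plan says.** The between-group analysis of normally distributed outcomes is one sentence in the Statistical Analysis section (printed twice): "2-way mixed Design MANOVA will be used to compare the groups for normally distributed data". Two further lines there complete it: "Pairwise multiple comparisons will be performed using the Bonferroni correction test" and "All tests are two-sided, and statistical significance will be set at" p < 0.05. Age and gender are the only other independent variables mentioned.

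The second factor of the two-way model is not named. From the Measurement methods section it must be visit: "Measurement will taken pretest assessment and posttest assessment and post one month follow up as follow". The X-ray section guarantees less for spur length: "Each patient should do at least two x-rays ,one before and another after".

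The design section reads "Double-blinded pretest posttest randomized control design will used". The third null hypothesis, on the difference between the two shockwave treatments, covers four outcomes and names no visit, change score or model term. Nowhere does the plan mention the group-by-time interaction, a primary visit or adjustment for the pretest.

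**The concern.** A two-way mixed model yields three effects: group, time and group-by-time. The one that by name compares the groups is the group main effect, and pairwise tests on the group factor compare means taken over every level of time. One of those levels precedes treatment, where randomised arms differ only by chance. That term therefore estimates a diluted version of the treatment difference and carries the chance pretest difference along with it.

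Two things are at stake. A real benefit may be under-estimated and, at moderate or high correlation between visits, missed more often. And because the plan names no term, the choice between group effect, interaction and single-visit comparison can be made after the results are seen.

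**Working it through.** The plan gives no effect size, SD, between-visit correlation, target power or sample-size calculation, so it has no figure of its own to reproduce.

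**Inputs from the documents.** Three visits (Measurement methods); at least two films for spur length (X-ray section); 20 per arm (Subjects: "this group composed of 20 subjects represented the experimental group 1"); two-sided 0.05. The Subjects section also says "Forty patients from both gender will be involved in this study and will randomly subdivided into two equal groups in number" and then lists three groups of 20. That conflict does not alter the 20 per arm used here.

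**Assumptions.** One outcome at a time; SD 1 at every visit; equal correlation r between visits; zero expected pretest difference; no dropout; the same effect d at posttest and at one month. Main case d = 0.8.

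**Step 1: what the group term estimates.**
- Three visits, constant effect: (0 + d + d)/3 = 2d/3.
- Two films only: (0 + d)/2 = d/2.
- Effect at only one post-treatment visit: d/3.
- Effect d/2 at posttest and d at one month: (0 + d/2 + d)/3 = d/2.

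**Step 2: variance per patient.**
- Mean of three visits: (1 + 2r)/3.
- Mean of the two post visits minus pretest: (1 + r)/2 + 1 − 2r = 1.5(1 − r).
- One post visit minus pretest: 2(1 − r).

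**Step 3: power.** Noncentral t, 38 df, noncentrality = (effect/SD) × √(20/2). At r = 0.5:
- Group term: (0.533/0.816) × 3.162 = 2.07, power 52%.
- Mean-post contrast: (0.8/0.866) × 3.162 = 2.92, power 81%.
- Single-visit change: (0.8/1) × 3.162 = 2.53, power 69%.

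| r | Group term | Mean post minus pretest | Single-visit change |
|---|---|---|---|
| 0 | 81% | 52% | 41% |
| 0.25 | 64% | 64% | 52% |
| 0.4 | 56% | 74% | 61% |
| 0.5 | 52% | 81% | 69% |
| 0.6 | 48% | 89% | 79% |
| 0.7 | 45% | 96% | 89% |

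The first two columns tie where (4/9)/[(1 + 2r)/3] = 1/[1.5(1 − r)], that is 4(1 − r) = 2(1 + 2r), so r = 0.25. At r = 0.5 the pair is 24% v 43% for d = 0.5 and 71% v 94% for d = 1.0.

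**Step 4: Bonferroni.** If three group pairs are tested, alpha is 0.05/3 = 0.0167. At d = 0.8 the group term and the mean-post contrast have 34% v 66% at r = 0.5, and 31% v 77% at r = 0.6.

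**Step 5: spur length with two films.** Group term: effect d/2, variance (1 + r)/2. Change: effect d, variance 2(1 − r). These tie at r = 0 (41% each). At d = 0.8 they give 30% v 69% at r = 0.5, and 27% v 89% at r = 0.7.

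**Step 6: pretest as covariate.** The adjusted mean of the two post visits has variance (1 + r)/2 − r². Standardised effects (effect/SD):
- r = 0: covariate d/√0.5 = 1.41d; group term 1.15d; mean-post contrast 0.82d.
- r = 0.25: covariate d/√0.5625 = 1.33d; the other two 0.94d each.
- r = 0.5: covariate d/√0.5 = 1.41d; group term 0.82d; mean-post contrast 1.15d.

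At each of these values the covariate version is the strongest.

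**The case against.** The best defence is that the plan never selects the group main effect. The same model supplies the interaction; a pretest-posttest design invites reading the result through change; the hypotheses on the effect of each treatment give the pretest a proper place in the time factor; and the Bonferroni comparisons could be between groups at each visit. All of this stands. A reader might infer that the plan has adopted the wrong test, but the text supports only that the test is unspecified and that its literal wording points to the diluted term.

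A reader might also infer that power is roughly halved. That holds only under particular values: at d = 0.8 it needs r of about 0.6 to 0.7, and the documents give neither quantity. There is no loss at r = 0.25, and the ordering reverses below it. The size also depends on the comparator. A change contrast at a single visit gains less than the mean-post contrast. So does the omnibus interaction F test: its noncentrality at r = 0.5 is 20 × (0.64/3)/0.5 = 8.53, the square of 2.92, but spread over two numerator df, so power is 73% rather than 81%.

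Finally, a reader might infer that a pretest imbalance produces false positives. Under randomisation that imbalance is part of the group term's error variance, and its type I error stays at 5%. The cost is noise and a diluted estimate.

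What the defence does not answer is the estimate itself. Even where power ties, the group term estimates 2d/3 and not d, and nothing in the plan rules out its use.

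**Conclusion.** The concern holds as a failure to name the treatment test, with a literal reading that leads to a diluted one. The dilution is to 2d/3 for a constant effect over three visits, and to d/2 for spur length if only two films exist. These factors rest on the pretest being a level of time, on randomisation, and on the stated pattern of effect.

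The power consequence is conditional. With d = 0.8 SD, 20 per arm and equal correlation, it runs from none at r = 0.25 to 45% v 96% at r = 0.7, with the advantage reversed at lower r. The figures are per outcome; the multivariate test over four outcomes would give different values. The plan should be changed, because the gap is easy to close and leaves the main comparison open to choice after the data are seen.

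**What to change.** State in the Statistical Analysis section that the between-group hypotheses are decided by one of these:

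- A named group-by-time contrast: for each outcome, the group difference in mean post-treatment value minus pretest. Report the group differences in change at posttest and at one month as well, each with a 95% CI.
- The group difference over the post-treatment visits with the pretest as covariate, and the pretest removed from the time factor.

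For spur length, say how many films enter the analysis; with two, the contrast is simply after minus before. Apply the Bonferroni pairwise tests to the chosen contrasts, and do not use a group main effect that includes the pretest for inference.

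The cost is SAP wording and, for the contrast version, different output from the same model; no new data are needed. The unadjusted change contrast loses some power if the correlation between visits is low (52% against 81% at r = 0 in the table above). The covariate version avoids that loss.
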